1.2 Test drug profile

- The drug to be developed is an acetylcholinesterase inhibitor donepezil hydrochloride (Aricept® Eisai), which is currently widely used as a treatment for dementia, and is intended to be converted into a treatment for fatigue and depression that are sequelae of COVID-19.
- In addition to COVID-19 sequelae, donepezil, the drug under development, has the potential to treat malaise and depression caused by viruses that damage the olfactory bulb, and may have applications in malaise, depression, and neuropathy caused by human herpesvirus 6 and influenza viruses.
 - As for competing drugs with the same mechanism of action, the relationship between COVID-19 sequelae and decreased acetylcholine production in the brain is itself a new discovery, so drug development from the perspective of this research plan has not been published.

172173174

175

176

177

178

179

170

171

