- 291 4.2 criterion (criteria) for selection
- Patients between 20 and 75 years of age at the time consent is obtained. 292 1)
- 293 2) Patients with COVID-19 infection who had upper respiratory tract symptoms or symptoms of fever or cough in the 294 acute phase.

- 295 3) Patients with a bivalent score ≥4 on the Chalder Fatigue Score-11 assessment in the previous observation period.
- $296 \qquad 4) \quad \text{Patients with confirmed positive COVID-19 infection by antigen or PCR test and within 52 weeks from COVID-19}$
- 297 onset to randomization.
- 298 5) Patients whose consent has been obtained from the patient.

- 300 < Rationale for setting
- 301 (1) The study was conducted in adults, and criteria were established to exclude patients in the later stages of life.
- 302 (2) to (4) Criteria were established for inclusion of subjects who were eligible for this study.
- 303 (5) Criteria were established for inclusion of patients who gave consent.

304

- 305 4.3 exclusion criteria
- 306 (1) Patients who have been previously diagnosed or suspected to have a psychiatric disorder that falls under F0 to F3 of
- 307 ICD-10, chronic fatigue syndrome, or other chronic illness associated with fatigue, and patients whose new-onset
- 308 depressive symptoms are not caused by COVID-19 but by the onset of a psychiatric disorder that falls
- 309 under F0 to F3 of ICD-10, and who have been diagnosed with a psychiatric disorder that falls under F0 to
- 310 F3 of ICD-10 The investigator believes that the new onset of depressive symptoms is not due to COVID-19
- 311 but is due to the onset of a psychiatric disorder that falls under ICD-10 F0-F3. (See Appendix 1 for ICD-
- 312 10 classification.)
- 313 2) Patients who are likely to start maintenance dialysis or dialysis during the study period.
- 314 3) Patients with Child-Pugh Classification C cirrhosis.
- 315 4) Patients with COPD, interstitial pneumonia, or other respiratory diseases (Hugh-Jones classification ≥ II).
- 316 5) Patients with heart failure (NYHA≥2).
- 317 6) Patients who are unable to answer the questionnaire in person (including those with cognitive decline).
- 318 7) Patients with influenza infection.
- 319 8) Patients already using donepezil or anticholinesterase inhibitors.
- 320 9) Patients who are allergic to any component of the investigational drug.
- 321 10) Patients with a history of hypersensitivity to piperidine derivatives.

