367 The investigator or collaborator registers eligible patients in Bellsystem24's Web Registration System for Limited Function 368 (hereinafter referred to as "Web Registration System"), and the investigator or collaborator prescribes the numbered 369 investigational drug for use to the subject. 370 371 5.1.3 Blinding and unlocking procedures 372 5.1.3.1 blinding 373 The donepezil and placebo groups will be double-blind and will remain blinded until the completion of the study for all 374 subjects. The investigational drug will be packaged in aluminum and the appearance of the study drug and placebo will be 375 indistinguishable. 376 377 5.1.3.2 Unblinding and unlocking procedure 378 The investigator may unblind the subject through the web-based registration system in an emergency. This must only 379 be used in emergency situations where the investigator must identify the investigational drug in order to provide 380 appropriate medical treatment to the subject or to ensure the safety of the subject. The reason for unblinding shall be 381 documented in the source documents and the case report form. 382 The investigator will inform the coordinating investigator and the coordinating office about the unblinded subjects. 383 384 Packaging and labeling of investigational drugs 385 The investigational drug will be delivered to each medical institution from SD Logistics Co. Packaging and labeling of 386 the study drug and placebo will be conducted in accordance with the principles of Good Manufacturing Practice (GMP) for 387 investigational new drugs. 388 For details on packaging and labeling, refer to the "Procedures for the Management of Investigational Drugs Used in 389 Clinical Trials. 390 391 5.1.5Storage conditions for investigational drugs 392 Investigational drugs should be stored at room temperature in a secure and controlled environment. Access to the 393 investigational products is limited to the investigator and authorized site personnel. 394 Any deviation from the temperature range of the investigational drug should be reported promptly in accordance with the 395 procedures for the management of investigational drug use. 396 397 5.1.6Clinical Trial Drug Management

Information regarding the prescription and return of investigational drugs for each subject in the study shall be recorded

on the Investigational Drugs Control Chart, which shall be used as the source document throughout the study period.

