Information on loss, damage (breakage, loss), non-use, and disposal by the subject of the investigational drug should also

be recorded in the chart. All records related to the transfer of investigational new drugs should be available for review at

398

399

400

401

402

any time throughout the clinical trial period.

104	5.2 Concomitant Drugs and Concomitant Therapy
405	Information on concomitant medications and concomitant therapies will be collected from the time of obtaining consent
406	to the end of the clinical trial.
407	
408	5.2.1 Concomitant medications/adjunctive therapy
109	Drugs other than concomitant use prohibited drugs, drugs other than concomitant use cautioned drugs, and treatments
410	other than concomitant use prohibited therapies may be taken or administered at the discretion of the investigator
411	(subinvestigator). However, only ultra-short-acting sleeping pills (zolpidem, zopiclone, eszopiclone) may be used.
412	
413	5.2.2 Prohibited drugs and prohibited therapies
414	Combination Prohibited Drugs
415	Antiepileptic, antipsychotic, antidepressant, anxiolytic, central stimulant, and antiparkinsonian drugs,
416	Use of antipyretics within 24 hours prior to conducting the preobservation period outcome symptom survey
417	Combination Prohibited Therapy
418	Repetitive transcranial magnetic stimulation (rTMS) therapy, nasopharyngeal abrasion therapy
419	Acupuncture and moxibustion do not fall under the category of concomitant prohibited therapy, but if they are practiced,
420	they should be noted in the case report.
421	
122	5.3 drug to be used in combination with
123	The following drugs should be used with caution, as they have been reported to increase or decrease the effect of
124	donepezil due to drug interactions. The investigator should decide whether or not to use these drugs.
125	Suisamethonium chloride hydrate
426	Choline activator
127	Cholinesterase inhibitor
128	Drugs that inhibit or induce CYP3A
129	Central anticholinergic agent
430	Atropine-type anticholinergic agent
431	Non-steroidal anti-inflammatory analgesics
132	
433	5.4 Confirmation of medication status
134	Unused investigational drugs, empty boxes, and empty bags will be collected at the 3-week visit after the start of
435	administration to check the medication status. If the patient is unable to visit the clinic, the medication will be collected
436	by mail.

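### Cholinesterase inhibitors, the test drug's own class, are barred at entry but only cautioned on study, so they may be started during dosing or follow-up

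*Protocol*

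**What the plan says.** - Section 1.2 states the class of the test drug: "The drug to be developed is an acetylcholinesterase inhibitor donepezil hydrochloride".
- Section 4.3, exclusion 8, removes at entry: "Patients already using donepezil or anticholinesterase inhibitors". The synopsis carries the same exclusion.
- Section 5.2.2 lists the prohibited drugs: "Antiepileptic, antipsychotic, antidepressant, anxiolytic, central stimulant, and antiparkinsonian drugs", plus antipyretics in the 24 hours before the baseline survey. Cholinesterase inhibitors and non-study donepezil are not listed.
- Section 5.3 lists "Cholinesterase inhibitor" among the caution drugs. The rule for that list is that they may alter the effect of "donepezil due to drug interactions. The investigator should decide whether or not to use these drugs".
- Section 5.2.1 deals with what is on neither list. Such drugs, and treatments "other than concomitant use prohibited therapies may be taken or administered at the discretion of the investigator", are allowed.
- Section 5.1.3.1 on blinding: "The donepezil and placebo groups will be double-blind and will remain blinded until the completion of the study for all" subjects.
- Section 5.2 on recording: "Information on concomitant medications and concomitant therapies will be collected from the time of obtaining consent" to the end of the trial, which 7.2.6 places at the 8-week follow-up.
- Section 8.2.1 names four events to be considered in the analysis: use of protocol-prohibited medication, treatment discontinuation, pregnancy and death.

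**The concern.** A placebo-controlled trial of a cholinesterase inhibitor should control use of other cholinesterase inhibitors at least as tightly as it controls other active drugs. Here the control is weaker. Section 5.2.2 prohibits antidepressants, which sections 1.1 and 1.4 describe as having little effect on these symptoms. The class that the trial's rationale (1.3) expects to work is left to judgement.

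Two things are at stake. The first is treatment contamination: a participant in either arm could take a drug of the test class outside the allocation, chiefly in the weeks between the end of study drug and the week-8 assessment. The second is double cholinesterase inhibition during dosing. An investigator who does not know the allocation may add a second drug of the class to blinded donepezil. The trial starts at 3 mg to look for gastrointestinal events (3.2), and it lists arrhythmia and gastrointestinal bleeding as notable adverse events (6.3.1.3).

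**Working it through.** The protocol gives no figure on this point, so the check is a reading of the rules side by side.

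**Step 1: is the class prohibited anywhere on study?** Section 5.2.2 does not name it. Section 5.3 names cholinesterase inhibitors but not donepezil. Since 1.2 places donepezil in that class, two readings of non-study donepezil are possible:

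- It is a caution drug under 5.3.
- If 5.3 covers only drugs taken alongside donepezil, it falls to general discretion under 5.2.1.

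It is prohibited on neither reading. Section 1.4.3 justifies placebo partly by the option of using drugs other than donepezil. That suggests outside donepezil was not intended, but it is rationale and not a prescribing rule. Discontinuation criterion 3 in 4.4 concerns subjects found after enrolment to be outside the scope of the trial. It does not clearly reach a drug that 5.3 allows.

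**Step 2: for how long?** Neither list has an end date. The one timed item in 5.2.2 is the antipyretic rule. Recording runs to the end of the trial and the trial ends at week 8, so the sound reading is that the permission lasts until then. This is an inference, not a stated rule.

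**Step 3: how is each case treated?**

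| Case | Prescribing rule | Event named in 8.2.1? |
|---|---|---|
| On the class at entry | Excluded (4.3, item 8) | Does not arise |
| Starts it during the 21 days, stays on study drug | Caution only (5.3) | No |
| Stops study drug early and switches to it | Caution or discretion (5.3, 5.2.1) | Yes, as treatment discontinuation |
| Finishes 21 days, starts it before week 8 | Caution or discretion (5.3, 5.2.1) | No |
| Starts an antidepressant at any time | Prohibited (5.2.2) | Yes, as prohibited medication |

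The gap is rows two and four. The last row shows how the protocol treats a drug class it regards as less relevant.

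**Step 4: can a statistical analysis plan close it?** Only in part. Section 8.2.1 does not call its list complete, so an analysis plan could add this event. It cannot change what an investigator is allowed to prescribe, which is set in section 5.

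**The case against.** The best defence is that the two rules do different jobs. Exclusion 8 removes established users, while 5.3 is an interaction precaution that places the class beside anticholinergics, CYP3A drugs and non-steroidal analgesics. A ban at entry with discretion for later medical need is a defensible design, and a flat ban would catch short-term medical use that the precaution may be meant to allow. This stands in part, and it is why the fix keeps a caution note. It does not explain why the test class gets discretion when antidepressants get a ban.

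Use is also likely to be very rare. Exclusion 1 removes ICD-10 F0 to F3 disorders, exclusion 6 removes patients with cognitive decline who cannot answer for themselves, age is capped below 75, and 1.2 calls the acetylcholine link a new discovery, so little prescribing for this purpose is to be expected. This stands, and it limits the size of the point.

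Safety is partly covered. Section 5.3 warns of the interaction, adverse events are collected at weeks 1, 3 and 8, dose increase depends on tolerability, the investigator may discontinue a subject, and emergency unblinding exists. These measures respond to harm or advise care. None prevents a blinded addition.

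A reader might infer more in three ways, and the protocol supports none of them:

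- *The off-drug period as a measure of bias.* Of the 56 days to week 8, 56 − 21 = 35 follow study drug. That is follow-up time, identical for any permitted drug, and it says nothing about how many patients use one.
- *Most secondary outcomes as affected.* Six of the eight secondary items are measured at week 8, but five of those six are also measured at week 3. Only the 8-week Chalder item is specific to week 8, and that scale at week 3 is the primary endpoint.
- *A known direction of bias or a loss of power.* Either would need rates of use by arm and an effect per user. The protocol gives neither, and nothing in it suggests that the rates would differ under blinding.

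**Conclusion.** The inconsistency is real and minor. The protocol bars the test drug's class at entry and then leaves it to a blinded investigator. Use during dosing alongside study drug, or after a completed course, falls outside the prohibited-medication event in 8.2.1.

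The effect is probably small, bears mainly on follow-up outcomes and on safety during dosing, and cannot be quantified from the protocol. The week-3 primary endpoint is little exposed. Use would be recorded under 5.2, so it would be visible afterwards.

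The conclusion rests on two assumptions: that the 5.2.2 and 5.3 rules run to the end of the trial, since no end date is given, and that no other trial document restricts prescribing of the class.

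**What to change.** 1. In 5.2.2, add donepezil other than study drug, and other cholinesterase inhibitors, as prohibited from consent through the week-8 assessment.
2. In 5.3, delete the cholinesterase inhibitor entry. Keep a caution note for medically necessary short-term use, stating that it is recorded as an intercurrent event.
3. Report any use by arm, from the concomitant-medication data that 5.2 already collects.

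Use then comes under the prohibited-medication event that 8.2.1 already names, so that section needs no new wording.

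The cost is one line added, one line replaced by a short note, and one item in the reporting. No new data are collected. The downside is that a patient who needs such a drug for another reason is counted as having an intercurrent event. The intention-to-treat estimate does not change by itself. The gain is in preventing contamination and double dosing, and in naming any use that still occurs.

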6.3 Adverse Event Assessment

adverse event should be considered as an adverse event.

- 562 6.3.1 Definition of adverse events
- An adverse event is any unwanted or unintended illness or symptom (including abnormal laboratory values) that occurs
 in a subject receiving an investigational drug, regardless of whether or not it is causally related to the investigational drug.
 The term "adverse event" means any unwanted or unintended illness or symptom (including abnormal laboratory test
 results) that occurs in a subject who is administered an investigational new drug, regardless of whether or not it is causally
 related to the investigational new drug. Adverse event" means an adverse event for which there is at least a reasonable
 possibility of a causal relationship with the investigational drug and a causal relationship cannot be ruled out.

- 570 6.3.1.1 adverse event
- Adverse events shall be as follows When multiple clinical symptoms or signs (including abnormal laboratory values) occur
- 572 in association with one adverse event (disease), they should be combined together as a single adverse event in the case
- 573 report in principle. If the investigator does not draw blood 3 weeks after the start of treatment or 8 weeks after the start
- of treatment for reasons such as inability to come to the hospital, the investigator will determine the adverse event based
- on the subject's condition and the presence or absence of symptoms.
- 576 Abnormal laboratory values or other safety tests that are considered clinically significant in the medical or scientific
- 577 judgment of the patient and that have been observed since the time consent was obtained.
- Aggravation of an event (symptom) that has already been chronically or intermittently observed.
- Signs, symptoms, or sequelae of suspected drug interactions
- The investigator determines that the event should be treated as an adverse event.

581	
582	6.3.1.2 Serious adverse events
583	Serious adverse events shall be as follows
584	(1) Death
585	(2) Obstacles
586	(3) Cases that may lead to death
587	(4) Cases that may lead to disability
588	(5) Cases requiring hospitalization or extended hospitalization at a hospital or clinic for treatment
589	6) Cases that are as serious as those listed in 1) through 5)
590	(7) Congenital diseases or anomalies in later generations
591	The "hospitalization" in 5) does not include hospitalizations (e.g., scheduled surgeries and examinations) for the sole
592	purpose of performing therapies or examinations that were planned prior to participation in the clinical trial during the
593	clinical trial. (However, any new occurrence during such hospitalization shall be treated as an adverse event.)
594	
595	6.3.1.3 Notable Adverse Events
596	If any of the following adverse events occur as noteworthy adverse events, the investigator should carefully observe
597	and appropriately treat the patient.
598	• arrhythmia
599	Myocardial infarction, heart failure
600	Gastrointestinal ulcer, gastrointestinal bleeding, gastrointestinal perforation
601	Hepatitis, jaundice
602	malignant syndrome
603	• dyspnea
604	acute pancreatitis
605	acute renal failure
606	Hypersensitivity (rash, itching)
607	Anorexia, nausea, vomiting
608	Diarrhea, abdominal pain, constipation
609	
610	6.3.1.4 Severity of adverse events
611	The investigator (sub)investigator will classify the severity of each adverse event/serious adverse event reported during
612	the clinical trial into one of the following categories.
613	Mild: Discomfort is minimal, tolerable, and does not interfere with daily activities.
614	Moderate: Event with definite discomfort that interferes with daily life.

Severe: An event that interferes with daily life.

6.3.1.5 Causal relationship with investigational drug

The investigator shall evaluate the causal relationship between the investigational drug and each adverse event/serious adverse event. The criteria shall be as follows

judgment	Definition.	
No relation	The event is clearly caused by a cause other than the investigational drug (e.g., disease, environment,	
	etc.). Or, there is no reasonable time-related relationship between the investigational drug and the event.	
Relevant.	The event is time-related to the onset of the event after administration of the investigational drug, and the	
	event attenuates with time after administration of the investigational drug, but recurs or worsens with	
	subsequent re-administration of the investigational drug.	

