- discretion of the investigator, depending on the condition of the subject. The investigator will then confirm whether the
- subject is eligible for the study and include the subject in the clinical trial. The items to be conducted during the pre-
- observation period will follow "7.1Visit Schedule".

735

- 736 7.2.4 Duration of investigational drug administration
- 737 The duration of study drug administration is 3 weeks. During the study drug administration period, subjects will
- 738 receiveeither donepezil or placebo. The protocol for the dosing period will follow "7.1Visit Schedule".

740 7.2.5 time of discontinuance

741 Patients who discontinue during the study period will be followed up either in clinic or via online clinic to perform a Visit

742 at Discontinuation. For patients who discontinue the study drug during the study period and are unable to come to the

743 hospital, the investigational drug remaining at home will be returned to the medical institution under the direction of the

investigator (subinvestigator). In addition, when follow-up is conducted by telephone, the investigator will instruct the

subject to come to the hospital if necessary if an adverse event is observed in the subject.

745746

744

747 7.2.6 Duration of follow-up and completion of the clinical trial

748 Subjects who have completed the study drug administration period will be followed up at 3 weeks and 8 weeks after the

start of the study drug administration in principle in the clinic. If it is difficult to visit the clinic, online follow-up is

acceptable. The study will be terminated at the 8-week follow-up.

751752

749

- 8 Statistical Analysis and Sample Size
- 753 8.1 null hypothesis and alternative hypothesis

754 The null hypothesis: there is no difference in a priori primary outcome between donepezil and placebo groups for

755 patients with mild to moderate COVID-19 disease.

756

- 757 8.2 analysis plan
- The primary endpoints are compared using t-tests and regression models, while other outcomes and observables are
- 759 compared using t-tests, Wilcoxon tests, $\chi 2$ tests, and regression models.

760

- 761 8.2.1 Treatment of Interim Events
- In this study, the use of concomitant medications prohibited by the study protocol, treatment discontinuation, pregnancy,
- and death will be treated as intermediary events and considered in the analysis.

764

- 765 8.2.2 Primary Objective Analysis
- 766 8.2.2.1 Sensitivity Analysis

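### The two causality categories in 6.3.1.5 leave some plausibly drug-related events with no category and conflict with 6.3.1; separately, Moderate and Severe overlap in 6.3.1.4

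*Protocol*

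**What the plan says.** **Causality (Protocol 6.3.1.5).** The investigator must judge every adverse event and serious adverse event, and there are two possible judgments.

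- *No relation* applies in either of two cases: "The event is clearly caused by a cause other than the investigational drug", or "there is no reasonable time-related relationship between the investigational drug and the event".
- *Relevant* applies when the event is related in time to the drug and the "event attenuates with time after administration of the investigational drug, but recurs or worsens with" "subsequent re-administration of the investigational drug". The conditions are joined, so all of them must be met.

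**Definition (Protocol 6.3.1).** After defining an adverse event, the section gives a second definition under the same term. It appears to be meant for an adverse reaction. It asks for at least a reasonable "possibility of a causal relationship with the investigational drug and a causal relationship cannot be ruled out". It does not mention re-administration.

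**Treatment (Protocol 5.1, 5.1.1, 7.1 and 7.2.4).** "The duration of study drug administration is 3 weeks", taken once daily with a dose increase after week 1. If the drug cannot be continued, the subject is discontinued. No section describes stopping the drug and starting it again. Adverse events are collected at weeks 1, 3 and 8 (6.3.2).

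**Severity (Protocol 6.3.1.4).** Each event goes into one of three grades. The upper two read "Moderate: Event with definite discomfort that interferes with daily life" and "Severe: An event that interferes with daily life". Section 6.2.2 uses the same scale for COVID-19 symptoms before treatment and at weeks 3 and 8.

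**The concern.** A classification rule should give every event exactly one category. The causality rule appears to leave some events with none, and the severity rule appears to give some events two.

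On causality, the condition that is hardest to meet is a pattern usually seen on rechallenge, and this trial plans one short course. Two sites could code the same event differently, one working from 6.3.1 and the other from 6.3.1.5. A site facing an event that fits neither category has to improvise.

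Adverse events are a secondary endpoint (2.1.3). Section 1.4.1 notes that the trial population differs from the one for which donepezil is approved and that risks will be discussed from this trial's results. What is at stake is the reliability of any summary by relatedness or by severity grade.

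**Working it through.** No sample size or error rate bears on this point, and the protocol gives no figure to reproduce. The check is logical: are the categories exhaustive, and are they mutually exclusive?

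**1. Causality: are the categories exhaustive?** For each event let

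- T = reasonable time relation to the drug
- C = clear other cause
- A = the event attenuates
- R = it recurs or worsens on re-administration

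As written in 6.3.1.5:

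- *No relation* = C or not-T
- *Relevant* = T and A and R

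The events that matter most have T true and C false, so *No relation* is ruled out. A and R can combine in 2 × 2 = 4 ways. Only one of these (A and R both true) is *Relevant*. The other three have no category. This counts patterns and says nothing about how often each occurs.

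Types of event with T true and C false that fall in the gap:

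| Event | Condition not met |
|---|---|
| Persists (6.3.1.6 has an outcome for ongoing events) | A |
| Occurs once and resolves | R |
| Leads to discontinuation | R, since no restart is described |
| Fatal (6.3.1.6 has an outcome for death) | A and R |
| Starts after the last dose | R, since no further dose is planned |

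The last row covers a long period. Follow-up runs to week 8 and dosing is planned for 3 weeks, so 8 − 3 = 5 weeks have no planned dosing.

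**2. Which events can meet *Relevant*?** Dosing is daily and the dose rises after week 1. An event that fades and then returns with a later daily dose, or worsens after the increase, can be read as satisfying R. The category is therefore not empty by construction.

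**3. Consistency with 6.3.1.** The second definition there turns on whether a causal relation is reasonably possible and cannot be excluded. Every row of the table could meet that standard, and none meets *Relevant* in 6.3.1.5. The two sections need to be reconciled.

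**4. Severity: are the grades mutually exclusive?** Let D = definite discomfort and I = interference with daily life.

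- *Moderate* = D and I
- *Severe* = I

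D and I together imply I, so every *Moderate* event is also *Severe*. No event is *Moderate* alone, although 6.3.1.4 requires a single grade. This affects grading only and has no bearing on relatedness.

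**The case against.** **Daily dosing is repeated administration.** A reader might infer that no event could ever be called related, because the trial has no rechallenge. The text does not support that. The rule says recurs *or worsens*. The drug is taken daily, a missed dose is taken the following day (5.1), and the dose rises after week 1. Intermittent nausea, for example, could qualify. This part of the objection stands, and it limits the point to the kinds of event in the table. It does not close the gap for them.

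**The text is a translation.** The English is visibly translated, and the second definition in 6.3.1 is garbled. A lost qualifier in *Severe* or a distorted connective in *Relevant* cannot be excluded, so this may not have been a deliberate design choice. That tempers any judgment of intent. Both definitions are nevertheless complete sentences and are the rule as it stands, so they still need correcting.

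**The consequences are contained.** This stands. Adverse events are defined and collected whatever their cause (6.3.1, 6.3.2). Serious events go to the head of the site and the coordinating investigator within 24 hours whatever the causal judgment (6.3.3.1). The blinded placebo arm allows event rates to be compared without any attribution. The protocol specifies no table of adverse reactions, so a prediction that such a table would be nearly empty goes beyond the text.

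**The link to a secondary endpoint is an inference.** A reader might conclude that the severity overlap damages an efficacy endpoint, because symptoms at weeks 3 and 8 are listed in 2.1.3. That endpoint names fatigue. Section 6.2.2 sits under safety assessment and lists cough, sputum, fever, taste disorder, anorexia and other items. The outcome symptom survey in 7.1 consists of the five questionnaires. The protocol does not state that the 6.2.2 grades form the endpoint, so all that can be said is that they use the same overlapping scale.

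**Conclusion.** The point holds in limited form. The causality categories in 6.3.1.5 are not exhaustive, and they conflict with the standard in 6.3.1. The severity grades in 6.3.1.4 are not mutually exclusive. These are two separate wording defects, and the second does not affect who is counted as having a drug-related event.

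No number of misclassified events can be derived, because the protocol gives no expected event rates or patterns. The direction is clear for causality: a literal reading of 6.3.1.5 withholds *Relevant* from events that 6.3.1 would count. The primary endpoint, the collection of adverse events and the reporting of serious events are unaffected.

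This rests on two assumptions: that the second definition in 6.3.1 was meant for adverse reactions, and that the conditions for *Relevant* are cumulative, as the sentence reads. The correction is worthwhile and inexpensive, but the validity of the trial does not depend on it.

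**What to change.** 1. **6.3.1.5.** Define *Relevant* by the 6.3.1 standard: a reasonable possibility of a causal relation that cannot be ruled out. State that any event not meeting *No relation* is *Relevant*, so that the two categories cover all events. Keep recurrence or worsening on re-administration as supporting evidence, not as a requirement.
2. **6.3.1.** Give the second definition its own term, so that it no longer redefines an adverse event.
3. **6.3.1.4.** Reword *Severe* so that it is distinct from and worse than *Moderate*, for example by a greater degree of interference with daily activities. The change carries over to the symptom grades in 6.2.2.
4. **Case report form guidance.** Align it with the new wording. If events have already been coded, review their causality and severity codes against it while the blind is kept.

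The cost is a wording amendment and a short instruction to sites. The downside is that more events will be counted as related, probably in both arms. The changes affect how events are recorded and leave the management of subjects as it is.
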